9.2.1 Relationship of AR/AE to study treatment

The causal relationship between an AE, especially SAE, or an AR and the study treatment will be evaluated by the lead investigators and the study center in Muenster.

Definitely related:	The AE/AR shows a substantial temporal and causal relationship to RT making other possibilities unlikely.
Probable:	The temporal and causal relationship between RT and the AE/AR is reasonable assumed but alternative explanations or causalities are not definitely ruled out.
Possible:	A temporal sequential relationship between AE/AR and RT is suggested but the clinical pattern of AE/AR is not typical .
Unlikely:	The relationship between RT and the occurred AE/AR is improbable and other medical conditions , therapies, diseases, medication or a lymphoma progression may better explain the AE/AR.
Not related:	The AE/AR shows no known chronological order or temporal relationship to RT and is most likely caused by another etiology .
Not assessable:	The available data does not permit to evaluate the relationship between AE/AR and study treatment.

In any case, the outcome of AE/AR whether causal relationship to treatment exists or not, has to be reported according to the following scheme.

Recovered/ Resolved:	Complete restoration of clinical state before AE/AR
Recovering/ Resolved:	Reduction in intensity of symptoms/signs already occurred suggesting a complete recovery during the further investigation
Not recovered/ Not resolved	Clinical condition of patient remains unchanged or worsened
Recovered resolved with sequel:	Incomplete resolving or resolution of AE/AR with persistent after-effects which should be graded
Fatal:	AE/AR leading to death (grade V toxicity, SAE, s. 9.2.3).
Unknown:	Incomplete or inconsistent information on outcome

9.2.2 Management of AR

All interventions (medication, treatments and therapies) aimed to improve/reduce AR are to be documented according to the following scheme:

None:	No actions taken
Medication:	Any drug use to counteract AR (also changes in prescribed amount of existent medication).
Other:	Any other measures taken, especially operative procedures

The remarks on simultaneous medication during the study period, as indicated under 8.2, have to be considered. Stimulating hematologic agencies as colony stimulating factor or erythropoietin are only allowed to ameliorate the respective cytopenia.

9.2.2.1 Changes in Radiotherapy

Greater changes in the RT-regime define a dropout for the individual patient and are to be reported to the lead investigators or study management within 2 working days:

Dose reduction:	Reduction in total/daily dose of RT not indicated in the study (e.g. a reduction from 2 to 1.8 Gy would be possible, a change of dose of at most 10% is possible)
Dose increase:	Dose increase beyond the indicated RT dosage of the treatment (a change of dose of at most 10% is possible)
Discontinuation:	Pause of RT treatment for one or several days additional to regular pauses (weekend, public holidays) (a pause of RT for at most 4 working days is possible)
Dropout:	see 9.2.3.1

Holds and restarts of radiation treatment can be made at the discretion of the treating physician. Any changes in procedure of RT and reasons therefore need to be reported to the lead investigators.

9.2.3 End of study

9.2.3.1 End of study for individual patients

There might be several conditions making it necessary for the patient to be taken out of the study:

- Excessive high grade toxicity (grade III or IV CTCAE)
- Withdrawal of informed consent for study participation of the patient (in that case, the patient is excluded)
- Treating physician's decision considering the general medical condition of the patient to end study
- Loss of contact to the patient
- Confirmed or suspected pregnancy
- Major violations of the study protocol (e.g. inability to adhere to the study schedule)
- Death of the patient

Each preliminary end of treatment has to be documented and patient is monitored concerning the remission status and overall survival as he/she is not included in the treatment analysis (per protocol).

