3.1 Objectives

3.1.1 Primary Objective

The primary objective is to demonstrate the efficacy and safety of the low-dose RT concept with 20 Gy (10x2 Gy). Therefore, the overall response rate (ORR) to radiation treatment is

examined to evaluate whether the interventional administration of 20 Gy is not relevantly inferior to international standard dose of 30 Gy.

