3.2.2 Secondary Endpoints

-**Quality of life** (QoL) according to EORTC (QLQ C30 and STO22), at baseline visit/ after 20 Gy (=last day of RT)/ 6 months after end of RT.

-**EFS**=Event-free survival (time from beginning of RT to any failure or death from any cause, all patients). Follow-up over 2 years after end of RT.

-**PFS**=Progression-free survival (time from beginning of RT to progression of lymphoma or death from any cause, patients in PR or SD). Follow-up over 2 years after end of RT.

-**RFS**=Recurrence-free survival (time from beginning of RT to recurrence of lymphoma or death from any cause, patients in CR). Follow-up over 2 years after end of RT.

-**LSS**=Lymphoma-specific survival (time from beginning of RT to death related to lymphoma or associated with the treatment, all patients). Follow-up over 2 years after end of RT.

-**OS**=Overall survival (time from beginning of RT to death from any cause, all patients). Follow-up over 2 years after end of RT.

-Level of **cytokines IL-1 β , IL-4, IL-8, TNF α** and other inflammation relevant molecules: **Syndecan1 and MMP-2** and **S100 proteins** at baseline visit/ after 4 Gy/ after 10 Gy/ after 20 Gy on last day of RT/ at 3 and 6 months after end of RT.

-**Acute toxicities** during treatment, 6 weeks after end of RT, according to NCI-CTC

-**Chronic toxicities** from 3 months up to 2 years after end of RT, according to NCI-CTC/ LENT-SOMA.

-Incidence of **Adverse Events** (AEs) and **Serious Adverse Events** (SAEs), continuously.

4 Study Design

-Single-arm, prospective, open label, interventional, multicenter study.

-Historic data from irradiated patients with indolent gastrointestinal lymphomas serves as a basis for the intended response rate.

-Participation of further international sites with expertise in radiation treatment of gastrointestinal lymphomas after approval of their Ethics Committee/ IRB.

-Number of 79 patients need to be analyzed.

-Justification for 'single-arm design' and for 'non-inferiority limit': the low prevalence of the disease, the limited risk of the study design (because of the option of renewed RT in case of persisting disease) and the benefit in terms of lower risk of adverse reactions due to the lower RT dose of 20 Gy in comparison to standard dose of 30 Gy.

5 Study Sites and Study Population

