8.3.2 FU-2 – FU-6

The further exams take place quarterly in the first year after treatment (FU-2 – FU-5), afterwards an annual visit is scheduled (FU-6).

FU-2:	3 months after end of RT ± 3 weeks
FU-3:	6 months after end of RT ± 3 weeks
FU-4:	9 months after end of RT ± 3 weeks
FU-5:	12 months (1 year) after end of RT ± 3 weeks
FU-6:	24 months (2 years) after end of RT ± 3 weeks

The FU-2 and FU-3 visits include blood draw!

At all follow-up visits (FU-2 – FU-6) chronic radiogenic reactions must be documented (see Appendix 16.6 Adverse Reactions according to LENT SOMA).

Each follow-up visit consists of the following examinations:

- Anamnesis
- Clinical examination: ECOG, weight, blood pressure
(at FU-1/-2/-3/-5/-6)
- Quality of life assessment with QLQ-C30 and STO-22 (at FU-1/-2/-3)
- Endoscopy/ Endosonography (+ biopsies) (at FU-2/-3/-5/-6)
- CT-imaging (at FU-3/-5/-6)
- **Blood draw (at FU-2/-3):**
 - o –Routine: small blood count, LDH, GOT, GPT, alcalic phosphatase, γ-GT, bilirubin, creatinine.
 - o –**Research program (analyses at the University of Muenster!):**
Two 7.5 - 9 ml serum monovettes.
Centrifugation, freezing and storage see 3.1.3 and Appendix 16.7 (SOP BLOOD SAMPLES for RESEARCH PROGRAM)
Transmission of frozen blood samples to Radiobiology lab, Muenster at the cost of Dept. of Radiation Oncology, University Hospital Muenster
- Chronic radiogenic reactions must be documented (see Appendix 16.6 Adverse Reactions according to LENT SOMA)

The FU-6 is the study termination visit and ends the study regularly.

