11.3 Statistical Analysis

The primary efficacy analysis will include all patients to be analyzed and will be performed according to the ITT principle. Primary analysis provides confirmatory statistical evidence. Further analyses will be regarded exploratory (hypothesis generating) and will be interpreted accordingly.

The primary endpoint, the OR rate 6 months after end of treatment, will be tested using one-sample binomial test for the non-inferiority hypothesis. The respective null hypothesis is $H_0: p \leq p_0 - \delta = 0.95 - 0.1 = 0.85$,

where p is the ORR of the interventional 20Gy treatment, $p_0=0.95$ is the assumed ORR of the standard 30Gy treatment based on historical data, and $\delta=0.1$ is the non-inferiority margin.

Beyond the ITT analysis of the primary outcome, sensitivity analyses will be performed. In per-protocol analyses only patients without major protocol violations are included.

Statistical analyses of the pre-specified secondary endpoints will be performed using descriptive and inductive statistical methods according to the type of variable.

Additional exploratory analyses will include model-based analyses, subgroup analyses, and safety analyses. In safety analyses all study patients that underwent radiation therapy will be included (safety population).

12 Data Sources and Data Management

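### Section 9.2.3.1 names only remission and overall survival for follow-up after early removal, so later toxicity and QoL data may be missing in the patients who tolerated RT worst

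*Protocol*

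**What the plan says.** Protocol section 9.2.3.1 lists conditions that may lead to a patient's removal. The first is "Excessive high grade toxicity (grade III or IV CTCAE". Others include physician decision and major protocol violation. Section 9.2.2.1 adds a route: larger changes to the RT regimen, beyond the stated tolerances of 10% in dose or 4 working days of pause, count as dropout, and its dropout entry refers to 9.2.3.1.

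For patients whose treatment ends early, 9.2.3.1 states that the "patient is monitored concerning the remission status and overall survival as he/she is not included in the treatment analysis (per protocol". Nothing else is named.

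The data at stake are defined elsewhere in the protocol:

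- Section 3.1.1: "The primary objective is to demonstrate the efficacy and safety of the low-dose RT concept with 20 Gy (10x2 Gy".
- Section 3.2.2: chronic toxicity is a secondary endpoint "from 3 months up to 2 years after end of RT, according to NCI-CTC/ LENT-SOMA", QoL is measured "at baseline visit/ after 20 Gy (=last day of RT)/ 6 months after end of RT", and AEs and SAEs are collected continuously.
- Section 8.3.2: "At all follow-up visits (FU-2 – FU-6) chronic radiogenic reactions must be documented".
- Section 11.3: "In safety analyses all study patients that underwent radiation therapy will be included (safety population".

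**The concern.** A patient removed for toxicity stays in the safety population, but the only sentence on that patient's further follow-up leaves out toxicity and QoL. A site that follows 9.2.3.1 as written could reasonably stop the chronic-toxicity forms and skip the 6-month questionnaire.

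The data would then be missing because of the outcome being measured. Late toxicity and 6-month QoL would be described mainly in patients who tolerated RT well. The error would favour 20 Gy, in a single-arm trial whose design is justified partly by an expected lower risk of adverse reactions (section 4). Analysis cannot repair this, because assessments that were never made cannot be recovered.

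**Working it through.** **Step 1. Does any section restore the missing assessments after removal?** The protocol states no figure on this point, so the check is textual.

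- *Section 9.2.1:* "In any case, the outcome of AE/AR whether causal relationship to treatment exists or not, has to be reported according to the following scheme". This secures the outcome of an event already reported, including graded sequelae. It does not schedule later toxicity assessments.
- *Section 9.2:* adverse reactions go on the acute and chronic forms during follow-up, and serious ones have reporting deadlines. This captures the event that led to removal. For later events it depends on follow-up continuing, which is the open question.
- *Section 8.3.2:* chronic reactions are documented at FU-2 to FU-6. It does not say whether a removed patient still has those visits.
- *Section 3.2.2:* continuous AE/SAE collection is stated as an endpoint, with no rule for removed patients.
- *Section 11.3:* this fixes who is in the safety population, not what is collected from them.
- *Section 8.4:* after study termination there are no scheduled examinations, and the annual report covers vital status, recurrence, and date and cause of death. It offers nothing on toxicity or QoL.

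No section expressly continues chronic-toxicity documentation, AE/SAE recording or the 6-month QoL. For QoL there is not even a provision pointing that way.

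**Step 2. What is not affected?** Remission is still followed in these patients, so the primary response rate and its test against 0.85 are untouched. The grade III/IV event behind the removal is already on record.

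**Step 3. How many patients?** Section 11.2 gives 83 assigned. The removal proportion g is an assumption, and all 83 are taken as irradiated.

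Patients without later data = 83 × g:

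- g = 2%: 83 × 0.02 = 1.66, about 2
- g = 5%: 83 × 0.05 = 4.15, about 4
- g = 10%: 83 × 0.10 = 8.3, about 8

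**Step 4. Illustration of the bias.** Assume a late severe toxicity rate of q0 = 3% in patients who stay and q1 = 20% or 40% in those removed, with all later data lost in the latter. None of these rates comes from the documents.

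True rate = g × q1 + (1 − g) × q0. The rate observed among those who stay is q0 = 3%. If removed patients remain in the denominator and are counted as event-free, the observed rate is (1 − g) × q0.

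| g | True, q1 = 20% | True, q1 = 40% | Observed, stayers only | Observed, all in denominator |
|---|---|---|---|---|
| 2% | 3.34% | 3.74% | 3.0% | 2.94% |
| 5% | 3.85% | 4.85% | 3.0% | 2.85% |
| 10% | 4.70% | 6.70% | 3.0% | 2.70% |

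The expected number of missed late cases, 83 × g × q1, runs from 83 × 0.02 × 0.20 = 0.3 to 83 × 0.10 × 0.40 = 3.3. The direction is the same in every row. The size follows entirely from the chosen inputs.

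**The case against.** The strongest reply is that silence is not a prohibition. The sentence in 9.2.3.1 opens with early end of treatment and explains itself by exclusion from the per-protocol analysis. It names two items without ending the others. It also follows a list that includes death, loss of contact and withdrawn consent, to which it cannot sensibly apply, so it is loosely drafted and should not be read as a strict limit. Remission is assessed by endoscopy at FU-2, FU-3, FU-5 and FU-6 and by CT at FU-3, FU-5 and FU-6. A patient still followed for remission would plausibly attend visits where the chronic-toxicity form is mandatory.

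Much of this stands, and it rules out several stronger conclusions that a reader might draw:

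- *That the protocol stops toxicity and QoL collection after removal.* It does not say so. It fails to say that collection continues.
- *That every patient with grade III/IV toxicity is removed.* The text says such conditions might arise and requires the toxicity to be excessive, so removal is a matter of judgement.
- *That the watch for accumulating grade 3 or 4 reactions (9.2, 9.2.3.2) loses these patients.* The triggering event and its outcome are reported and count. Only later events, including those graded on LENT SOMA, are at risk.
- *That the primary result is biased.* Section 3.1.1 examines its objective through the response rate, and remission is still followed.

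The reply does not remove the gap. Attendance for endoscopy is not an instruction to complete toxicity forms, and nothing covers the 6-month QoL. Nor can the matter be left to a statistical analysis plan, because it concerns what sites collect.

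**Conclusion.** The point holds as a gap in the data-collection rule, of moderate severity. Section 9.2.3.1 names remission and overall survival alone for patients who end early. It does not fit with the all-irradiated safety population in 11.3 or with the toxicity and QoL endpoints in 3.2.2. The data at risk are later toxicity, later AEs/SAEs and 6-month QoL, with losses concentrated in poorly tolerating patients and a bias towards lower reported late toxicity.

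The size cannot be derived from the documents. About 2 to 8 patients is the range if 2% to 10% of 83 are removed. Any statement of how far the late-toxicity rate would be understated also needs assumed late rates and complete loss of later data, so it is illustrative only. Late toxicity and QoL are secondary, and section 11.3 treats everything beyond the primary analysis as exploratory. That limits the consequence, although safety is named in the primary objective.

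**What to change.** In section 9.2.3.1, separate ending or changing RT from leaving the study. State that every irradiated patient, whatever the reason for ending or changing treatment, continues FU-1 to FU-6 with acute and chronic toxicity forms, AE/SAE recording and the 6-month QoL, unless consent to further data collection is withdrawn. Apply the same wording to dropouts under 9.2.2.1. Exclusion from the per-protocol analysis can stay as it is. This brings 9.2.3.1 into agreement with 3.2.2 and 11.3.

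The cost is small, because the visits, forms and questionnaires already exist. The downside is a few more completed forms and possibly a less favourable reported toxicity rate. No change is proposed to when treatment is stopped.

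### Sections 9.2.3.1 and 11.3 do not give the same per-protocol set, and one natural reading of 9.2.3.1 makes exclusion depend partly on outcome

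*Protocol*

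**What the plan says.** Protocol section 11.3 (Statistical Analysis) makes the ITT analysis of the 6-month ORR primary and confirmatory and treats everything further as exploratory. Sensitivity analyses of the primary outcome are announced, and the only one described is per-protocol: "In per-protocol analyses only patients without major protocol violations are included".

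Protocol section 9.2.3.1 (End of study for individual patients) lists seven reasons why a patient may have to leave the study: high-grade toxicity, withdrawal of consent, physician decision, loss of contact, pregnancy, major violation and death. Four of them bear on this point:

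- "Excessive high grade toxicity (grade III or IV CTCAE")
- "Treating physician's decision considering the general medical condition of the patient to end study"
- "Major violations of the study protocol (e.g. inability to adhere to the study schedule")
- "Death of the patient"

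The sentence that closes the section reads "Each preliminary end of treatment has to be documented and patient is monitored concerning the remission status and overall survival", and goes on to say that "he/she is not included in the treatment analysis (per protocol").

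Section 9.2.2.1 (Changes in Radiotherapy) is linked to this. It calls larger changes in RT a dropout, tolerates dose changes of up to 10% and pauses of up to 4 working days, and refers to 9.2.3.1 for dropout.

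**The concern.** The two sections state two rules for one analysis set. Because 9.2.3.1 lists major violation separately from toxicity, physician decision and death, the protocol itself treats these as different things. A patient who leaves for one of the other reasons, with no violation, belongs to the per-protocol set under 11.3 but may be outside it under 9.2.3.1.

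Some of the extra reasons are related to outcome. A patient who dies, or whose condition worsens until the physician ends participation, is less likely to have a documented response at 6 months than one who stays. Removing such patients tends to raise the per-protocol ORR. In a non-inferiority trial that is the favourable direction, so the analysis meant to test the claim could seem to support it.

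The trial is single-arm and open-label. If the text allows two sets, the choice between them could be made after responses are known.

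**Working it through.** **1. The design figure reproduces.** Inputs from section 11.2: reference and assumed ORR 0.95, margin 0.10 (so the null rate is 0.85), one-sided alpha 2.5%, power 80%.

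n = [1.960·√(0.85·0.15) + 0.842·√(0.95·0.05)]² / 0.10² = 78.02, rounded up to 79, as stated. The exact test with 79 patients succeeds at 74 or more responders, with true alpha 0.0156 and power 0.797. With all 83 assigned patients in the denominator it succeeds at 78 or more. Either way at most 5 failures are allowed, so a single patient can matter.

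**2. The two rules side by side.** The narrow reading takes the 9.2.3.1 sentence literally, as covering early end of treatment. The broad reading takes it as the consequence of the whole list.

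| Patient | Section 11.3 | 9.2.3.1, narrow | 9.2.3.1, broad |
|---|---|---|---|
| Major protocol violation | out | out only if RT stopped early | out |
| RT stopped early for toxicity | not stated; depends on what counts as a major violation | out | out |
| Completed 20 Gy, then died before month 6 | in | in | out |
| Completed 20 Gy, then withdrawn by the physician before month 6 | in | in | out |

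The narrow reading conflicts with 11.3 only over patients who stop RT early without a major violation, and it largely overlaps with the RT-delivery deviations of 9.2.2.1. The broad reading differs clearly in the last two rows.

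**3. What one exclusion can do.** The figures are one-sided 97.5% Clopper-Pearson lower limits, set against 0.85. The counts are illustrative, since the protocol gives no removal rate by reason.

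| Before | Lower limit | One non-responder dropped | Lower limit |
|---|---|---|---|
| 77/83 (92.8%) | 0.849 | 77/82 (93.9%) | 0.863 |
| 73/79 (92.4%) | 0.842 | 73/78 (93.6%) | 0.857 |

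In both rows the limit crosses 0.85.

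**4. The direction is not fixed.** Suppose the removed patients are responders. Starting from 78/83 (94.0%, limit 0.865), dropping four responders gives 74/79 (93.7%, limit 0.858). The ORR falls slightly.

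**The case against.** The strongest reply is that the exclusion sentence is triggered by early end of treatment, and treatment is a two-week RT course. A patient who completed 20 Gy and later died did not end treatment early. The sentence also provides for continued monitoring of remission status, which suits a patient who stopped RT and cannot apply to one who has died. On this reading few deaths are dropped and the overlap with RT-delivery deviations is large. This stands as a fair literal reading, and it limits the size of the problem. It does not settle the matter. The sentence sits under an end-of-study heading, directly after a list that includes death, and it is the only stated consequence of that list for the analysis.

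A reader might infer that the per-protocol ORR can only move upward. The protocol does not support that. Non-response and progression are not listed reasons, and a patient removed for toxicity, pregnancy or loss of contact may be a responder.

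A reader might also infer that the trial's conclusion is at risk. It is not: the ITT analysis is confirmatory and the per-protocol analysis has no success rule of its own, so a favourable per-protocol figure cannot reverse a failed ITT test.

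Finally, a detailed list of major violations is commonly left to an SAP, and its absence is no fault here. The point is that the protocol already states two rules, and an SAP would have to override one of them.

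**Conclusion.** The point holds in a limited form. Sections 9.2.3.1 and 11.3 do not define the same per-protocol set. How far they differ depends on the reading: little if 9.2.3.1 means early end of RT, more if it means any listed reason for leaving the study. On the broader reading some exclusions follow from outcome and would tend to raise the ORR, without doing so in every case.

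The confirmatory result is untouched. What is weakened is the only sensitivity analysis described for the non-inferiority claim, where one excluded non-responder can carry the lower limit from just below 0.85 to above it. That size rests on illustrative counts near the boundary; the documents do not say how many patients would be removed or how many of them would be non-responders. It should be corrected, but it does not call the design into question.

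**What to change.** Reconcile the two passages. Delete the per-protocol clause from the closing sentence of 9.2.3.1, keep its monitoring requirement, and let 11.3 govern. In 11.3, state that patients are excluded from the per-protocol set only for eligibility violations and major deviations in RT delivery, and that membership is decided before response is reviewed.

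Patients who completed protocol RT and later died or were withdrawn then stay in the set. They are analysed with the remission status that 9.2.3.1 already collects, or as non-responders if none exists.

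The cost is one sentence in 9.2.3.1 and matching wording in 11.3. No new data are needed, and the reasons for taking a patient off study or treatment stay as they are. The downside is that the per-protocol ORR may be slightly less favourable.
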